7. STATISTICS AND DATA ANALYSIS

The key study indicators are based on the WHO NCD Global Monitoring Framework (Appendix 1). Therefore, we will follow the operational definition of the indicators, method of estimation, and guidelines for data disaggregation (by sex/socio-demographic stratifiers) proposed in the framework. As we will use a multistage sampling approach, appropriate sample weight will be estimated and used during the descriptive analysis.

Data will be analysed using appropriate statistical software (eg STATA, SPSS). Continuous variables will be assessed for normality, and non-normally distributed variables will be transformed as appropriate or will be assessed using non-parametric tests if appropriate. The data and samples collected will enable both cross-sectional and longitudinal analyses, and thus to define the prevalence and incidence of clinical outcomes of interest respectively. We will quantify the relationship between the clinical outcomes of interest, and potential underlying exposures (lifestyle, environmental, genetic) risk factors using regression techniques. For the assessment of relationship between a continuous primary and secondary outcome we will carry out mixed models analysis of covariance (e.g., BP, HbA1c, blood cholesterol, serum creatinine) etc. Mixed models logistic regression will be used to assess the association between explanatory and categorical outcome variables (e.g., T2D, CVD, hypertension, hypercholesterolemia). Regional differences within and between countries will also be explored. Statistical significance will be inferred at P<0.05, using techniques (eg Bonferroni) to control for multiple comparisons where appropriate. Power estimates for analyses of cross-sectional and longitudinal outcomes data are summarized in **Tables 4 and 5**.

Table 4. Power calculations for cross-sectional analyses. Results are expressed as i. the precision with which the prevalence for a clinical outcome of interest can be quantified and ii. the odds ratios (OR) detectable for association between a clinical outcome and an underlying exposure (exposure prevalence 20%, power 90%, P<0.05). Precision and power estimates are provide overall (N~160,000 people), at the level of the country (M~30,000 people), or at the level of the site (N~750 people). The table also summarized precision and power for low (~1%), intermediate (5-10%) and high frequency (~20-30%) outcomes of interest.

			Precision	OR detectable		
Outcome measure	Expected prevalence	Overall	Country	Site	Overall	Country
N=		160,000	30,000	750	160,000	30,000
Hypertension Diabetes	30% 20%	0.2% 0.2%	0.5% 0.5%	3.3% 2.9%	1.04 1.05	1.10 1.12
Chronic kidney disease	10%	0.1%	0.3%	2.2%	1.07	1.16

Cardiovascular disease	5%	0.1%	0.3%	1.6%	1.09	1.23
Severe CKD	2%	0.1%	0.2%	1.0%	1.14	1.37
Stroke	1%	0.0%	0.1%	0.7%	1.20	1.54

Table 5. Power calculations for longitudinal outcomes. Table summarises the expected incidence of disease endpoints in South Asians (per 100,000 participants/year, based on follow-up of South Asians in the LOLIPOP study [2003-2017]), and thus the expected number of disease cases that occur after 5 and 10 years in the population sample of up to 160,000 South Asians proposed in the current surveillance project. Relative risks detectable are provided for a range of diseases in a nested case control study (2 controls per case, 90% power), under 3 experimental designs: i. single marker study (SMS, P<0.05), ii. Metabolome wide association study (MWAS, P<10⁻⁵) and iii. Genome-wide association study (GWAS, P<5x10⁻⁸). Power is calculated based on an exposure present in 20% of the population, or minor allele frequency 20% for genetic association.

Disease	Incidence (per 100K	•	ected ises	RR: SMS		RR: MWAS		RR: GWAS	
	year)	5 yrs	10 yrs	5 yrs	10 yrs	5 yrs	10 yrs	5 yrs	10 yrs
Type 2 diabetes	950	8550	17100	1.09	1.06	1.19	1.13	1.17	1.11
CVD	864	7776	15552	1.09	1.06	1.20	1.14	1.17	1.11
Cancer (all cause)	625	5625	11250	1.11	1.08	1.24	1.16	1.20	1.14
Myocardial infarction	453	4077	8154	1.14	1.09	1.28	1.19	1.23	1.16
Stroke	221	1989	3978	1.19	1.14	1.42	1.19	1.34	1.24
Breast cancer (F)	251	2259	4518	1.26	1.19	1.58	1.39	1.47	1.32
Prostate cancer (M)	158	1422	2844	1.34	1.23	1.77	1.51	1.62	1.42
Colo-rectal cancer	47	423	846	1.45	1.31	2.07	1.69	1.85	1.56
Pancreatic cancer	22	198	396	1.71	1.47	2.81	2.12	2.42	1.89
ESRF	15	135	270	1.89	1.59	3.43	2.45	2.88	2.14

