2. STUDY OBJECTIVES

This project represents a collaboration between academic and clinical experts in NCD prevention and control from leading institutions in Bangladesh, India, Pakistan, Sri Lanka and the UK. With initial 4-year funding from the UK National Institutes for Health Research, we will pursue a program of translational research in South Asian that aims to:

- Strengthen NCD surveillance systems in Bangladesh, India, Pakistan and Sri Lanka, by establishing a network of >200 surveillance sites across these South Asian countries.
- Using standardised approaches, complete structured assessments on a representative sample of ~160,000 South Asian men and women aged 18+ years, living at the >200 surveillance sites. Collect and store biological samples for epidemiological purposes.
- In the longer-term, continue longitudinal follow-up of the 160,000 people screened, to ascertain fatal and non-fatal NCD outcomes. Thereby enable quantification of NCD risk relationships, including identification and evaluation of disease biomarkers.
- In addition, use a subset of the surveillance sites as Health observatories for evaluation of healthcare interventions targeted at improving prevention and control of T2D and CVD in South Asia.
- Thereby provide the first robust, nationally representative data on the burden of T2D, CVD and their risk factors, and on the quality of care for these major NCDs to quantify needs, in South Asian populations.
- Disseminate the data to relevant stakeholders, include health service providers and policy makers to inform resource allocation and health system priorities. In addition, use the clinical data and biological samples collected, to pursue epidemiological research into aetiological mechanisms underlying the increased risk of T2D and CVD in South Asians.

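### All 20 expected-case counts in Table 5 are computed for 180,000 people instead of the stated 160,000 (12.5% too high), and the breast and prostate counts conflict with their own relative risks

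*Protocol*

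**What the plan says.** The cohort size is consistent in the text. Section 2 plans to "complete structured assessments on a representative sample of ~160,000 South Asian men and women aged 18+ years". Section 3 repeats about 160,000, and the regional targets in Table 1 (section 4) add up to it: 30,000 + 30,000 + 40,000 + 30,000 + 30,000 = 160,000.

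Section 7 uses this figure for both power tables. The Table 4 legend reads "Precision and power estimates are provide overall (N~160,000 people", with "exposure prevalence 20%, power 90%, P<0.05" for the odds ratios. The Table 5 caption promises the "expected number of disease cases that occur after 5 and 10 years in the population sample of up to 160,000 South Asians", with incidence given per 100,000 participants per year. Detectable relative risks are for a nested case-control design with two controls per case, 90% power and 20% exposure. They are given at three significance levels: single marker (SMS, 0.05), metabolome-wide (MWAS, 10⁻⁵) and genome-wide (GWAS, 5×10⁻⁸).

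Two Table 5 rows are marked as applying to one sex: breast cancer (F) and prostate cancer (M).

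**The concern.** The printed counts do not follow from the printed incidence and the stated cohort. For type 2 diabetes, 950 per 100,000 per year over 5 years in 160,000 people gives 7,600; the table has 8,550.

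The two single-sex rows raise a second problem. Breast cancer has more printed 5-year cases than stroke (2,259 against 1,989) but a larger detectable relative risk in all three 5-year columns: 1.26 against 1.19, 1.58 against 1.42, and 1.47 against 1.34. Under one common design, more cases must give a smaller detectable effect, so the counts and the relative risks in these rows cannot rest on the same number of cases.

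Table 5 is the protocol's only quantitative support for the longitudinal and biomarker objectives. Anyone judging what the stored samples can deliver would start from these counts.

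**Working it through.** **1. Reproducing the Table 5 counts.** Inputs: incidence and cases from Table 5; formula: cases = N × incidence × years / 100,000. Solving for N:

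- Type 2 diabetes: 8,550 / (950 × 5) × 100,000 = 180,000; 17,100 / (950 × 10) × 100,000 = 180,000.
- Stroke: 1,989 / (221 × 5) × 100,000 = 180,000.
- The other rows give exactly 180,000 at both horizons, including breast (251 × 9 = 2,259) and prostate (158 × 9 = 1,422).

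A cumulative-risk formula does not explain the counts: 180,000 × (1 − (1 − 0.0095)⁵) = 8,389, not 8,550.

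**2. The counts at 160,000.** The multiplier is 8 at 5 years and 16 at 10 years. The excess is 180,000/160,000 = 1.125, or 12.5%.

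| Disease | Printed, 5 / 10 years | At 160,000, 5 / 10 years |
|---|---|---|
| Type 2 diabetes | 8,550 / 17,100 | 7,600 / 15,200 |
| CVD | 7,776 / 15,552 | 6,912 / 13,824 |
| All cancer | 5,625 / 11,250 | 5,000 / 10,000 |
| Myocardial infarction | 4,077 / 8,154 | 3,624 / 7,248 |
| Stroke | 1,989 / 3,978 | 1,768 / 3,536 |
| Colorectal cancer | 423 / 846 | 376 / 752 |
| Pancreatic cancer | 198 / 396 | 176 / 352 |
| ESRF | 135 / 270 | 120 / 240 |

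**3. Breast and prostate.** I solved the 5-year MWAS relative risks for the number of cases needed, using a two-sided two-proportion test with pooled variance, two controls per case, 20% exposure in controls, 90% power, and the relative risk treated as an odds ratio. In the other eight rows the answer is 1.09 to 1.13 times the printed count. For breast it is about 1,259 (0.56 times) and for prostate about 784 (0.55 times), half the ratio seen elsewhere.

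- If the rates are sex-specific and half the cohort is female: breast 251 × 0.8 × 5 = 1,004 and prostate 158 × 0.8 × 5 = 632. The printed counts are 2.25 times these, or 125% too high. With women at 40% to 60% of the cohort, the excess runs from 181% down to 87.5% for breast and from 87.5% up to 181% for prostate.
- If the rates are per all participants: breast 251 × 8 = 2,008 and prostate 158 × 8 = 1,264. The counts are 12.5% too high, and the relative risks conflict with them.

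**4. Do the printed relative risks follow from the printed counts?** Not by this calculation. The 5-year SMS values in the eight other rows would need 1.35 to 1.66 times the printed cases; for type 2 diabetes the printed 8,550 cases give 1.11, not 1.09. The 10-year MWAS value for stroke, 1.19, also looks wrong: 3,978 cases give about 1.30.

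**5. Table 4 overall odds ratios.** Same test, with N × prevalence cases and the rest of the cohort as controls, two-sided 0.05 and 90% power:

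| Prevalence | Printed | At 160,000 | At 180,000 |
|---|---|---|---|
| 30% | 1.04 | 1.045 | 1.042 |
| 20% | 1.05 | 1.052 | 1.049 |
| 10% | 1.07 | 1.069 | 1.065 |
| 5% | 1.09 | 1.096 | 1.090 |
| 2% | 1.14 | 1.152 | 1.143 |
| 1% | 1.20 | 1.217 | 1.204 |

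Only the last three rows separate the two sizes. At 160,000 the printed odds ratios there have about 86%, 85% and 85% power. At 30,000 the method gives 1.106, 1.122, 1.164, 1.230, 1.372 and 1.547 for the country column, against 1.10, 1.12, 1.16, 1.23, 1.37 and 1.54 printed.

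**6. Type 2 diabetes at risk.** Table 4 expects 20% prevalence. If 950 applies only to people free of diabetes, 160,000 × 0.8 × 0.0095 × 5 = 6,080 cases.

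**The case against.** No sample size, recruitment target or decision rule is derived from Table 5. Long-term follow-up is itself described as pending funding. Moving from 180,000 to 160,000 changes the recomputed 5-year SMS relative risks only slightly: type 2 diabetes 1.11 to 1.12, stroke 1.24 to 1.26, ESRF 2.16 to 2.26. This stands: no objective becomes infeasible. It does not rescue the counts, which exceed the ceiling set in their own caption.

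Four stronger readings are tempting and are not supported:

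- **That every detectable relative risk is too optimistic.** The printed relative risks do not follow from the printed counts, so which N lies behind them cannot be settled. The breast and prostate values already behave as if about half the cases were used.
- **That Table 4 was computed at 180,000.** This is a best-fit inference from two-decimal figures. The gap is 0.01 to 0.02 in three rows, sidedness is not stated, and the same formula misses two country values in rounding. A one-sided test at 160,000 fits five of the six overall values, although it fails the country column (1.49 against 1.54 for stroke).
- **That 125% is established.** It needs sex-specific rates and an equal sex split. The protocol states neither, and the caption's unit is per participants. The sex labels and the halved relative risks favour that reading without proving it.
- **That the diabetes row must use 80% of the cohort, or that ignoring loss to follow-up is an arithmetic error.** The first depends on the denominator of an external rate that the protocol does not give. The second is a planning refinement in a table framed as an upper limit.

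**Conclusion.** Wrong as written. The use of 180,000 in all 20 Table 5 counts is exact arithmetic, and the 12.5% overstatement against the protocol's own 160,000 needs no assumption. The conflict between counts and relative risks in the breast and prostate rows is also certain. Its size is not: 125% for an equal sex split and sex-specific rates, 87.5% to 181% if women make up 40% to 60%, and 12.5% if the rates are per all participants. The Table 4 discrepancy is probable and small. The 6,080 figure for type 2 diabetes is conditional on the denominator of the rate. The practical effect on detectable effects is modest.

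**What to change.** In section 7:

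1. Recompute all Table 5 counts at 160,000, or state and justify another N throughout the protocol.
2. For breast and prostate cancer, use women only and men only with a stated sex split, or state that the rates are per all participants.
3. Re-derive all SMS, MWAS and GWAS columns from the corrected counts, naming the method and sidedness. Check the 10-year MWAS value for stroke in particular.
4. Check the N behind the Table 4 overall odds ratios. At 160,000, two-sided, the last three rows become about 1.10, 1.15 and 1.22.
5. State whether the type 2 diabetes incidence applies to all participants or only to those free of diabetes at baseline.

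The cost is a desk recalculation of two tables. Recruitment, procedures and data collection are unaffected; the case counts become less favourable.

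### Protocol Table 5: the 10-year stroke MWAS relative risk (1.19) is wrong, and 16 of the 20 single-marker entries have about 75% power, not 90%, at 2 controls per case

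*Protocol*

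**What the plan says.** Section 7 of the protocol offers Table 5 as the power estimates for longitudinal outcomes. One design statement covers the whole table: "Relative risks detectable are provided for a range of diseases in a nested case control study (2 controls per case, 90% power". Three significance levels follow: "single marker study (SMS, P<0.05", "Metabolome wide association study (MWAS, P<10⁻⁵" and "Genome-wide association study (GWAS, P<5x10⁻⁸". The exposure assumption is "Power is calculated based on an exposure present in 20% of the population, or minor allele frequency 20% for genetic association".

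Two rows matter most:
- "Stroke 221 1989 3978 1.19 1.14 1.42 1.19 1.34 1.24"
- "Myocardial infarction 453 4077 8154 1.14 1.09 1.28 1.19 1.23 1.16"

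The columns are incidence per 100,000 per year, expected cases at 5 and 10 years, then the relative risk (RR) at 5 and 10 years for SMS, MWAS and GWAS in turn. The table does not say whether the tests are one- or two-sided, which test the GWAS column uses, or what denominator applies to the two sex-specific cancers.

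**The concern.** With alpha, power, control ratio and exposure all fixed, the detectable RR depends only on the number of cases. Equal case counts must give nearly equal RRs within a column, and a row with fewer cases must show a larger RR. The 10-year stroke MWAS cell breaks this rule. The SMS column also looks too small beside the MWAS column for the two to share one design and one power.

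Quantifying risk relationships and evaluating biomarkers is an objective in section 2, and section 10 describes the stored samples as a limited resource that can be used up. A nested case-control study sized from these cells would have less than the 90% power claimed, and for 10-year stroke metabolomics far less.

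**Working it through.** **Inputs (Table 5 and its legend).** Control exposure p0 = 0.20; 2 controls per case; power 90%; alpha 0.05 (SMS) or 10⁻⁵ (MWAS), taken as two-sided; printed case counts.

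**Formulas.** Exposure among cases: p1 = RR·p0 / (1 + p0(RR − 1)). With n cases and 2n controls:
- pooled proportion p̄ = (p1 + 2p0)/3
- SE0 = √[p̄(1 − p̄)(1/n + 1/2n)]
- SE1 = √[p1(1 − p1)/n + p0(1 − p0)/2n]
- power = Φ[(p1 − p0 − z·SE0)/SE1]

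**Case counts.** Stroke at 5 years: 221 × 5 × 1.8 = 1,989, as printed. The printed counts therefore correspond to 180,000 people. The stated 160,000 gives 8/9 of them, so stroke at 10 years becomes 221 × 10 × 1.6 = 3,536.

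**(a) Stroke, MWAS, 10 years.** No formula is needed to see the conflict:

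| Row | Cases | MWAS RR | GWAS RR |
|---|---|---|---|
| MI, 5 years | 4,077 | 1.28 | 1.23 |
| Stroke, 10 years | 3,978 | 1.19 | 1.24 |
| MI, 10 years | 8,154 | 1.19 | 1.16 |

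Stroke at 10 years has slightly fewer cases than MI at 5 years but carries the MI figure that rests on twice as many. In every other pair the MWAS value exceeds the GWAS value.

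Power at 1.19:
- p1 = 0.238/1.038 = 0.2293; p̄ = 0.2098
- SE0 = 0.00791; SE1 = 0.00803; z = 4.417
- (0.0293 − 4.417 × 0.00791)/0.00803 = −0.70, so power is **24%**

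With 3,536 cases it is 18%. Solving for 90% gives RR **1.30** (1.32 with 3,536 cases).

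**(b) SMS column.** Worked example, ESRF at 5 years (135 cases, RR 1.89):
- p1 = 0.378/1.178 = 0.3209; SE0 = 0.0450; SE1 = 0.0470
- (0.1209 − 1.960 × 0.0450)/0.0470 = 0.69, so power is 76%

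The same calculation for all rows, on the printed cases:

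| Row | Printed RR, 5/10 y | Power, 5/10 y | RR for 90%, 5/10 y |
|---|---|---|---|
| Type 2 diabetes (T2D) | 1.09/1.06 | 75%/71% | 1.11/1.08 |
| CVD | 1.09/1.06 | 71%/67% | 1.12/1.08 |
| Cancer, all | 1.11/1.08 | 74%/77% | 1.14/1.10 |
| MI | 1.14/1.09 | 80%/73% | 1.16/1.11 |
| Stroke | 1.19/1.14 | 74%/79% | 1.24/1.17 |
| Colorectal | 1.45/1.31 | 75%/76% | 1.57/1.38 |
| Pancreatic | 1.71/1.47 | 76%/76% | 1.91/1.59 |
| ESRF | 1.89/1.59 | 76%/76% | 2.16/1.75 |
| Breast | 1.26/1.19 | 96.0%/97.5% | 1.22/1.16 |
| Prostate | 1.34/1.23 | 96.4%/96.1% | 1.29/1.20 |

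The 16 entries outside breast and prostate run from 67% to 80%, mean 74.8%. With cases scaled to 160,000 they run from 62% to 75%. The breast and prostate entries fall to 75-79% only if their cases are halved for sex.

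**(c) Do the columns share one design?** MWAS entries outside the 10-year stroke cell and the breast and prostate rows have about 81-85% power, against about 75% for SMS.

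A second check barely depends on the choice of test. With the same cases and controls, ln(RR SMS)/ln(RR MWAS) should be about (1.960 + 1.282)/(4.417 + 1.282) = 0.57. The printed 5-year values give T2D 0.50, stroke 0.50, colorectal 0.51 and ESRF 0.52.

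**The case against.** **The test may differ from the one assumed.** One-sided testing gives 77-87% for the 16 SMS entries, 4 controls per case gives 75-87%, and taking every RR at the top of its rounding interval gives at most 82%. For the stroke cell, one-sided testing gives 29% and 4 controls per case 37%. None reaches 90%.

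**RR might mean a ratio of exposure frequencies** (p1 = RR × 0.20). SMS power is then 86-97%. But the 90% value for ESRF at 5 years would be 1.75, not 1.89, MWAS and GWAS power would be 99% or more, and the stroke cell would still have only 64%. This reading does not rescue the table.

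**A reader might infer that the whole SMS column is too small.** It is not: on their printed cases the four breast and prostate entries are too large.

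**A reader might also infer that the SMS column used the entire cohort as controls.** Some cells fit, such as stroke at 5 years (1.194 against 1.19). Others do not, even with 180,000 people: CVD at 10 years would be 1.070 (printed 1.06) and pancreatic at 5 years 1.693 (printed 1.71). Three controls per case with 80% power fits about as well (T2D 1.090/1.063, stroke 1.192, colorectal 1.447 at 5 years). The document does not settle the cause. Relabelling the comparison group would not repair the column either: at 160,000, ESRF at 5 years would be 1.939 against 1.89.

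**Materiality is limited, and this stands.** For common outcomes the SMS shift on printed cases is 0.02-0.03. The recruitment targets in section 4 are set by region and not derived from Table 5, and section 3 makes long-term follow-up depend on funding.

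**Conclusion.** The point holds in two parts. The 10-year stroke MWAS entry is wrong on the table's own evidence: about 24% power at 1.19, with about 1.30 needed. Separately, 16 of the 20 SMS entries have 67-80% power against the stated 90%. The gap is small for common outcomes and large for rare ones (colorectal 1.45 against 1.57, ESRF 1.89 against 2.16, both at 5 years). The breast and prostate rows do not match their printed case counts, and the SMS and MWAS columns do not share one design and power.

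The power figures assume a two-sided, unmatched two-proportion test with 20% exposure in controls. The internal contradiction in the stroke row needs none of these assumptions. Someone might conclude that the cohort itself is too small; the document does not support that, because its size is not derived from this table. What is wrong is the stated performance of later nested studies.

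**What to change.** Correct the 10-year stroke MWAS cell to about 1.30 on the printed cases, or 1.32 at 160,000. Then recalculate all three columns with 2 controls per case and 90% power on one case-count basis: the stated 160,000. State sidedness, the GWAS test, and the denominator for breast and prostate cancer. Recalculating only the SMS column would leave the table on mixed bases.

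SMS values at 160,000, two-sided (5/10 years):
- T2D 1.12/1.08
- CVD 1.12/1.09
- Cancer 1.15/1.10
- MI 1.17/1.12
- Stroke 1.26/1.18
- Colorectal 1.61/1.41
- Pancreatic 1.98/1.64
- ESRF 2.26/1.80
- If half the cohort is of each sex and the sex-specific cases are halved accordingly: breast 1.35/1.24, prostate 1.45/1.31

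The cost is one recalculated table with slightly less favourable figures. Recruitment, sampling and procedures do not change.

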8. REGULATORY ISSUES

8.1 ETHICS APPROVAL

The Chief Investigator has obtained approval from Imperial College Research Ethics Committee. The study will be conducted in accordance with the recommendations for physicians involved in research on human subjects adopted by the 18th World Medical Assembly, Helsinki 1964 and later revisions.

8.2 CONSENT

Informed written consent will be obtained from each participant before their enrolment, facilitated by videos in relevant languages and bilingual translators. As noted above, participants identified to have significant health conditions (e.g. T2D, hypertension) will be referred to an appropriate facility for counselling and treatment.

8.3 CONFIDENTIALITY

The Chief Investigator will preserve the confidentiality of participants taking part in the study and fulfil transparency requirements under the General Data Protection Regulation for health and care research

8.4 INDEMNITY

Imperial College London holds negligent harm and non-negligent harm insurance policies which apply to this study.

